## 6.2 Treatment arms

Subjects will be assigned to CFZ533 or matching placebo according to a 1:1 randomization scheme, as follows:

- CFZ533 10 mg/kg IV infusion every 28 days (q4w), for a treatment duration of 24 weeks (6 doses).
- CFZ533 matching placebo IV infusion every 28 days (q4w), for a treatment duration of 24 weeks (6 doses).

Both infusions (drug and vehicle) will be at matched volumes, constant rates, and given over 2 hours. In case of any adverse event please refer to [Section 6.8](#) treatment of adverse events.

## 6.3 Permitted dose adjustments and interruptions of study treatment

Study drug dose adjustments or interruptions are not permitted. In case of an AE or for any reason (e.g., non-compliance, operational hurdle) resulting in a deviation from the required dosing scheme, agreement with Novartis will be necessary to decide whether the subject can continue or needs to be discontinued from the study.

## 6.4 Treatment assignment

Prior to dosing, eligible patients will be randomized via an IRT system to one of the two treatment arms. Randomization numbers will be generated in ascending, sequential order by a validated IRT system.

The site personnel (e.g. PI or delegate or unblinded pharmacist) will log into the IRT system to randomize the patient. The IRT will then assign a randomization number to the patient and will indicate to the unblinded site personnel the treatment to be assigned to the patient.

The screening number will be maintained as unique identifier for each patient throughout the study and will be entered into the CRF (details in the SOM). The randomization numbers will be generated using the following procedure to ensure that treatment assignment is unbiased and concealed from patients and from the blinded site staff. A patient randomization list will be produced by a Contract research Organisation (CRO) using a validated system that automates the random assignment of treatment arms.

The patient randomization list will be reviewed and approved by a member of the Novartis randomization office. After approval the randomization list will be integrated into the IRT system.

Patients will not be replaced.

## 6.5 Treatment blinding

This is a double blind study: subjects, investigators performing the assessments and data analysts will remain blind to the identity of study treatments according to the specifications provided in Appendix 3 of the SOM. Randomization data are kept strictly confidential, and are accessible only to authorized personnel, until unblinding of the trial.

The identity of the treatments will be concealed by the use of study drugs that are all identical in packaging, labeling, schedule of administration, appearance, taste and odor.

The bioanalyst will request a copy of the randomization to facilitate analysis of the samples. The bioanalyst will provide the sample data to the team under blinded conditions. The bioanalyst will keep this information confidential until IA or final clinical database lock.

Corporate Confidential Information

The DMC will receive unblinded data as described in the DMC charter.

Corporate Confidential Information

Otherwise, unblinding will only occur in the case of patient emergencies ([Section 6.6](#)), at the time of the IA and C the conclusion of the study.

## 6.6 Emergency breaking of assigned treatment code

Emergency unblinding should only be undertaken when it is essential to treat the subject safely and efficaciously. Most often, study treatment discontinuation and knowledge of the possible treatment assignments are sufficient to treat a study subject who presents with an emergency condition. Emergency unblinding of a patient is managed via the IRT system. Study site personnel will be trained on the Emergency Unblinding Procedure in IRT prior to study start. **The unblinded treatment code should not be recorded on the CRF.** The investigator must also immediately inform the Novartis local monitor that a patient has been unblinded. Unblinded patients will be discontinued from the study.

If appropriate, the investigator will inform the subject how to contact his/her trained backup in cases of emergency when he/she is unavailable.

An assessment will be done by the appropriate site personnel and the Sponsor after an emergency unblinding to assess whether or not study drug should be discontinued for a given subject and, if applicable, whether the subject can continue into the next trial phase.

## 6.7 Treatment exposure and compliance

Compliance with treatment administration will be collected in the eCRF. Exposure to CFZ533 will be measured by appropriate PK parameters as detailed in [Section 8.5](#).

## 6.8 Recommended treatment of adverse events

Parenteral administration of monoclonal antibodies can be associated with acute, severe reactions (occurring within the first few hours post dose) secondary to hypersensitivity, immunogenicity, or ADCC-mediated cell depletion.

In this study, CFZ533 will be administered as a 2-hour infusion. No systemic infusion reactions have been noted with CFZ533 in healthy volunteers or RA patients (Study CCFZ533X2101); however, investigators should be aware of the possibility and be prepared to treat such events.

In case of any signs of an acute reaction, clinical treatment will be provided as determined by the treating physician on a case-by-case basis and depending on the severity, using symptomatic treatment, antihistamines, NSAIDs, acetaminophen, intravenous fluids, corticosteroids, or adrenaline. Patients will be monitored at the site for at least 6 hours post dose or longer at the discretion of the Investigator to ensure adequate safety monitoring.

For the management of allergic reaction, anaphylaxis and cytokine release, it is recommended to follow the guidelines by the National Cancer Institute Common Toxicity Criteria (NCI-CTCAE/v4.03, Reference <http://evs.nci.nih.gov/ftp1/CTCAE/About.html>).

Medication used to treat AEs must be recorded on the Concomitant medications/Significant non-drug therapies CRF.

## 6.9 Rescue medication

Rescue therapy (IVIg or plasma exchange) is instituted due to worsening of myasthenic weakness that in the opinion of the treating physician requires immediate therapy. This usually involves acute worsening of oropharyngeal or respiratory function so that compromise of the airway or ventilator function is judged to be imminent.

In case of rescue therapy, study treatment should be discontinued but the patient can remain in the study or for the safety follow-up period or at least complete the EoS visit (Visit 777) assessments.

Use of rescue medication must be recorded on the Concomitant medications/Significant non-drug therapies CRF after start of study drug.

## 6.10 Concomitant treatment

Patients should remain on their standard of care therapies (if not prohibited) and dose should be maintained stable, unless changes are judged to be necessary based on history and clinical examination after discussion between the investigator and Novartis.

## Corticosteroid

If the patient is on oral corticosteroids, methotrexate or tacrolimus at screening the dose must be stable for at least **1 month** prior to randomization.

For patients that are receiving corticosteroids, a predefined steroid tapering (Table 6-1) will be allowed after achievement of MM state (Jaretzki et al 2000). In patients whose disease substantially worsens after tapering, the previous steroid dose will be reinstated, and no further dose reduction will be attempted in the study.

**Table 6-1** Predefined tapering scheme

Baseline daily dose (x)*	Week 13	Week 17	Week 21	After Week 25
$x \leq 10$ mg	No change	No change	↓ by 2.5 mg	As needed #
$10 < x \leq 20$ mg	No change	↓ by 2.5 mg	↓ by 2.5 mg	As needed #
$x > 20$ mg	↓ by 5 mg	↓ by 5 mg	↓ by 2.5 mg	As needed #

\* Or equivalent alternate day dose

# According to usual standard of care

↓ Decrease

## Immunosuppressant or immunomodulatory drugs

In addition to corticosteroids, only one immunosuppressant or immunomodulatory drug **at a stable dose** is allowed during the study. Azathioprine and mycophenolate mofetil must be at a stable dose for at least 4 months prior to randomization. Cyclosporin should be at a stable dose for at least 3 months prior to randomization.

## Cholinesterase inhibitors

Patients on cholinesterase inhibitors must be on a stable dose for at least 2 weeks prior to randomization.

Cholinesterase inhibitors **will be held at least 12 hours prior** to QMG and MGC testing at each study visit. It may be necessary for patients to remain overnight at the study site for observation during this time, if the investigator deems it necessary.

## Other concomitant medications

All prescription medications, over-the-counter drugs and significant non-drug therapies (including physical therapy and blood transfusions) administered or taken within the timeframe defined in the entry criteria prior to the start of the study and during the study, must be recorded on the Concomitant medications/Significant non-drug therapies section of the CRF. Medication entries should be specific to trade name, the single dose and unit, the frequency and route of administration, the start and discontinuation date and the reason for therapy.

## 7 Discontinuation and study completion

### 7.1 Discontinuation of study treatment

Patients may voluntarily discontinue the study treatment for any reason at any time.

The Investigator should discontinue study treatment for a given patient if, on balance, he/she believes that continuation would be detrimental to the subject's well-being.

- Study treatment **must** be discontinued and patients followed up for safety, if possible, if the following occur:
- In case of non-detectable AChR or MuSK autoantibodies for patients enrolled prior to this amendment.
- Significant increase in MG disease activity requiring treatment outside of a clinical trial setting.
- Worsening of MG with severe oropharyngeal or respiratory weakness (MGFA class IVb or V).
- Rescue medication use (IVIg or plasma exchange).
- Pregnancy.
- Severe or life threatening infusion reaction.
- Major worsening of renal function (e.g. >40% increase from baseline creatinine level).
- Acute infection as a severe AE as judged by the investigator.
- Major elevations (>4.0 x ULN) in amylase or lipase or any abnormal signs or symptoms suggesting pancreatic injury.
- Significant changes in standard coagulation parameters, including prothrombin time (PT), activated partial thromboplastin time (aPTT) suggesting an increased risk for hypercoagulability or any sign or symptom of a TE.
- Any other AE or complication where continued dosing of the patient is considered to be placing them at excess risk.
- Patient withdraws consent (when patient must also be withdrawn from the study).

Patients who are withdrawn from the study for any reason will not be replaced.

Study patients who discontinue participation for any reason or who decide they do not wish to participate in the study further should not be considered withdrawn from the study unless they withdraw their consent (see [Section 7.3](#)). Where possible, they should return for their EoS visit assessments (Visit 777). If they fail to return for these assessments for unknown reasons, every effort (e.g. telephone, e-mail, letter) should be made to contact them as specified in [Section 7.2.1](#). Any unresolved AEs will be followed by the investigator until resolution.

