#### 8.4.4 Laboratory evaluations

In the case where a laboratory assessment that is listed in the inclusion/exclusion criteria is outside of a **protocol-specified range** at screening (Visit 1 or 2), the assessment may be repeated once prior to randomization. If the repeat value remains outside of protocol-specified ranges, the subject is excluded from the study.

In the case where a laboratory range is outside the reference range for the laboratory at screening or baseline, a decision regarding whether the result is of clinical significance or not shall be made by the Investigator and shall be based, in part, upon the nature and degree of the observed abnormality. The assessment may be repeated once prior to randomization.

In all cases, the Investigator must document in the source documents, the clinical considerations (i.e., result was/was not clinically significant and/or medically relevant) in allowing or disallowing the subject to continue in the study.

Clinically relevant deviations of laboratory test results occurring during or at completion of the study must be reported and discussed with Novartis personnel. The results should be evaluated for criteria defining an adverse event and reported as such if the criteria are met. Repeated evaluations are mandatory until normalization of the result(s) or until the change is no longer clinically relevant. In case of doubt, Novartis personnel should again be contacted.

The blood sample for hematology and clinical chemistry should be taken in fasting conditions.

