**Table 9-2 Follow Up Requirements for Liver Events and Laboratory Triggers**

Criteria	Actions required	Follow-up monitoring
Potential Hy's Law case a	Discontinue the study drug immediately Hospitalize, if clinically appropriate Establish causality Complete liver CRF	ALT, AST, TBL, Alb, PT/INR, ALP and γGT until resolution c (frequency at investigator discretion)
ALT or AST > 8 × ULN	Discontinue the study drug immediately Hospitalize if clinically appropriate Establish causality Complete liver CRF	ALT, AST, TBL, Alb, PT/INR, ALP and γGT until resolution c (frequency at investigator discretion)
> 3 × ULN and INR > 1.5	Discontinue the study drug immediately Hospitalize, if clinically appropriate Establish causality Complete liver CRF	ALT, AST, TBL, Alb, PT/INR, ALP and γGT until resolution c (frequency at investigator discretion)
> 5 to ≤ 8 × ULN	Repeat LFT within 48 hours If elevation persists, continue follow-up monitoring If elevation persists for more than 2 weeks , discontinue the study drug Establish causality Complete liver CRF	ALT, AST, TBL, Alb, PT/INR, ALP and γGT until resolution c (frequency at investigator discretion)
> 3 × ULN accompanied by symptoms b	Discontinue the study drug immediately Hospitalize if clinically appropriate Establish causality Complete liver CRF	ALT, AST, TBL, Alb, PT/INR, ALP and γGT until resolution c (frequency at investigator discretion)
> 3 to ≤ 5 × ULN (patient is asymptomatic)	Repeat LFT within the next week If elevation is confirmed, initiate close observation of the patient	Investigator discretion Monitor LFT within 1 to 4 weeks

Criteria	Actions required	Follow-up monitoring
ALP (isolated)		
> 2 × ULN (in the absence of known bone pathology)	Repeat LFT within 48 hours If elevation persists, establish causality Complete liver CRF	Investigator discretion Monitor LFT within 1 to 4 weeks or at next visit
TBL (isolated)		
> 2 × ULN (in the absence of known Gilbert syndrome)	Repeat LFT within 48 hours If elevation persists, discontinue the study drug immediately Hospitalize if clinically appropriate Establish causality Complete liver CRF	ALT, AST, TBL, Alb, PT/INR, ALP and γGT until resolution c (frequency at investigator discretion) Test for hemolysis (e.g. reticulocytes, haptoglobin, unconjugated [indirect] bilirubin)

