## 9.4 Renal safety monitoring

Renal events are defined as one of the following:

- confirmed (after ≥ 24h) increase in serum creatinine of ≥ 25% compared to baseline during normal hydration status
- new onset (≥1+) proteinuria, hematuria or glucosuria; or as a
- doubling in the urinary albumin-creatinine ratio (ACR) or urinary protein-creatinine ratio (PCR) (if applicable).

The following two categories of abnormalities/adverse events have to be considered during the course of the study:

- serum creatinine triggers that will require follow up and repeat assessments of the abnormal laboratory parameter
- urine dipstick triggers that will require follow up and repeat assessments of the abnormal laboratory parameter

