**Table 9-3 Specific Renal Alert Criteria and Actions**

Renal Event	Actions
Serum creatinine increase 25 – 49% compared to baseline	Confirm 25% increase after 24-48h Follow up within 2-5 days
Serum creatinine increase $\geq$ 50 % compared to baseline	Follow up within 24-48h if possible Consider drug interruption Consider patient hospitalization /specialized treatment
Albumin- or Protein-creatinine ratio increase $\geq$ 2-fold	Confirm value after 24-48h Perform urine microscopy
Albumin-creatinine ratio (ACR) $\geq$ 30 mg/g or $\geq$ 3 mg/mmol; New dipstick proteinuria $\geq$ 1+	Consider drug interruption / discontinuation
Protein-creatinine ratio (PCR) $\geq$ 150 mg/g or $>$ 15 mg/mmol	
New dipstick glucosuria $\geq$ 1+ not due to diabetes	Blood glucose (fasting) Perform serum creatinine, ACR
New dipstick hematuria not due to trauma	Urine sediment microscopy Perform serum creatinine, ACR
Document contributing factors: co-medication, other co-morbid conditions, and additional diagnostic procedures performed in the CRF	
Monitor patient regularly (frequency at investigator's discretion) until one of the following:	
Event resolution: (sCr within 10% of baseline or protein-creatinine ratio within 50% of baseline)	
Event stabilization: sCr level with $\pm$ 10% variability over last 6 months or protein-creatinine ratio stabilization at a new level with $\pm$ 50% variability over last 6 months.	

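### For every creatinine rise above 40%, Table 9-3 names a weaker action on study drug than the mandatory stop in Section 7.1

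*Protocol*

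**What the plan says.** Protocol Section 7.1 contains a list of events after which study treatment has to be discontinued and the patient followed for safety where possible. One entry is "Major worsening of renal function (e.g. >40% increase from baseline creatinine level". The percentage illustrates what counts as major; it is not written as a fixed limit.

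Section 9.4 deals with renal monitoring. It defines a creatinine event as a rise of at least 25% from baseline, confirmed after at least 24 hours during normal hydration. It describes "serum creatinine triggers that will require follow up and repeat assessments of the abnormal laboratory parameter". Table 9-3 then assigns actions in two creatinine rows:

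- Rise of 25-49%: "Confirm 25% increase after 24-48h Follow up within 2-5 days".
- Rise of 50% or more: "Follow up within 24-48h if possible Consider drug interruption Consider patient hospitalization /specialized treatment".

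Neither Section 9.4 nor the table refers to Section 7.1.

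Two other provisions bear on the point. Section 6.3 says "Study drug dose adjustments or interruptions are not permitted" and requires sponsor agreement on whether a patient may continue after any departure from the dosing scheme. Section 8.4.4 says that clinically relevant laboratory deviations "must be reported and discussed with Novartis personnel".

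**The concern.** Section 7.1 and Table 9-3 both measure renal function by percentage rise in creatinine from baseline, so a site can hold one laboratory value against both. Above 40% it gets two answers: a mandatory stop from the discontinuation section, and from the action table either nothing about study drug or an invitation to consider interrupting it. Staff handling an abnormal creatinine are likely to open the renal action table, and nothing there sends them back to Section 7.1.

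Two things are at stake. A patient who meets the protocol's own illustration of a mandatory stop could be kept on treatment, or only interrupted, at a site that works from the table. Renal discontinuations could also vary between sites for reasons unrelated to the patients. Safety and tolerability is the first primary objective (Section 2.1), and Section 3.6 asks investigators to watch for changes in renal function and acute kidney injury.

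**Working it through.** No sample size, power or event figure is involved, so the check sets the rules side by side. The 7.1 example, a rise above 40%, is a ratio to baseline above 1.40. The table rows correspond to ratios of 1.25-1.49 and of 1.50 or more, reading the table in whole percentages.

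| Creatinine rise from baseline | Section 7.1 | Table 9-3: action on study drug | Table 9-3: other actions |
|---|---|---|---|
| 25-40% | Example not met | None | Confirm after 24-48 h; follow up in 2-5 days |
| 41-49% | Example met: must discontinue | None | Same as the row above |
| 50% or more | Example met: must discontinue | Consider interruption | Follow up within 24-48 h if possible; consider hospitalization or specialized treatment |

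1. Up to 40% the two provisions agree: the example is not reached and the table asks for confirmation and follow-up.
2. The 25-49% row straddles the 7.1 example. Its upper part, 41-49%, exceeds the example but carries the same instruction as a 25% rise.
3. Every rise of 50% or more also exceeds 40%. The only drug action named there is optional, and it is interruption, not discontinuation.
4. That optional action also sits badly with Section 6.3, which does not permit interruption and sends any dosing deviation to the sponsor. The upper row therefore names neither the action that 7.1 requires nor one the site may take by itself.
5. The confirmation condition differs too. Section 9.4 requires a repeat after at least 24 hours under normal hydration before a rise counts as a renal event. Section 7.1 states no such condition, so a site cannot tell whether one unconfirmed value above 40% should end treatment.

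On time available: doses are 28 days apart, each with a window of 2 days either side, so two consecutive doses are at least 28 - 4 = 24 days apart. If the table's confirmation (at most 48 hours) and follow-up (at most 5 days) run one after the other, they take at most 2 + 5 = 7 days. For a result received just after an infusion, that leaves at least 24 - 7 = 17 days before the next dose. The margin shrinks if the result arrives late in the dosing interval.

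On trial size: Section 11.6 randomizes 44 to obtain 36 evaluable, an allowance of 44 - 36 = 8. Patients are not replaced, so each additional renal stop would use at most one of those 8.

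**The case against.** The strongest reply is that no rule is missing. Section 7.1 is explicit and mandatory, nothing in Table 9-3 releases a site from it, and a site that reads both can comply by stopping. That stands, and it sets the size of the point. A reader might infer that the protocol allows dosing to continue above 40%, or that the table overrides Section 7.1. The documents do not support either reading.

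The 40% figure is an example, so a reader should not infer that a single value of 41% requires an immediate permanent stop. Section 9.4 asks for confirmation under normal hydration, and confirming before stopping is a reasonable reading of 7.1. This argues for putting the confirmation condition in both places. It does not explain why the table never reaches a stop, however large or well confirmed the rise.

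Sponsor involvement also reduces the risk. A site that interrupts must take the question of continuing to the sponsor under 6.3, and relevant laboratory deviations must be discussed under 8.4.4. The 28-day interval usually gives time for this, and ongoing safety review, a study-level renal stopping rule (Section 7.4) and a DMC stand behind it. These safeguards make a missed stop less likely but leave the two texts unequal. Section 9.6 says that stopping criteria are presented above, which could mean either Section 7.1 or Table 9-3 and so settles nothing.

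Two comparisons should not be drawn. The liver table (Table 9-2) states stops in its rows, and a reader might infer that the renal table is deficient by that standard. But 7.1 lists no liver criterion, so the liver stops have to be stated elsewhere, while the renal stop already stands in 7.1. A reader might also note that "Consider drug interruption / discontinuation" appears beside the albumin and protein findings and infer that proteinuria is treated more strictly than a large creatinine rise. That depends on the layout of a table extracted from PDF, and the conclusion here does not use it.

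**Conclusion.** The inconsistency is real and modest. For every creatinine rise above 40%, the action table names a weaker step on study drug than Section 7.1 requires: none at 41-49%, and optional interruption at 50% or more. The conclusion rests on the texts as they stand and on taking the 7.1 example at face value. It assumes only that some sites will act from the renal table without returning to 7.1. The documents give no renal event rate, so the number of patients exposed to the discrepancy cannot be estimated; it may be zero. No efficacy analysis or sample size figure is affected. The change should be made because it concerns a mandatory safety stop and costs little.

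**What to change.** Use one cutoff and one condition in both places.

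- **Table 9-3, rise of 25-40%:** confirm after 24-48 hours and follow up within 2-5 days, as now.
- **Table 9-3, rise above 40%:** withhold further dosing and repeat within 24-48 hours under normal hydration. If confirmed, discontinue study treatment per Section 7.1 and consider hospitalization or specialized treatment. Delete the suggestion to consider drug interruption from the creatinine row.
- **Section 7.1:** state the renal criterion as a confirmed (after at least 24 hours, normal hydration) increase of more than 40% from baseline creatinine. The investigator's general power to stop for the patient's well-being stays as it is.

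If the clinical team prefers another cutoff, the same number and confirmation condition should appear in both sections. Because the repeat is due within 48 hours and doses are 28 days apart, withholding will seldom delay an infusion. If it does, the sponsor agreement in Section 6.3 applies.

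The cost is a wording amendment and a note to sites. The repeat test uses the 24-48 hour timing already in the table. There may be a few more discontinuations at sites that had followed the table alone. Requiring confirmation keeps one transient value from ending a patient's treatment.
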